10.6 Data management

IQVIA (who will perform the PASS on behalf of AstraZeneca) will take responsibility for application for the study permits, obtaining necessary approvals (ethical or otherwise), and access to the study data. Generally, the data will be stored and analysed in accordance with local policy. All data used in this study will be in the form of electronic records, and the data holders collect and manage data according to their own standards.

The identification of the study population will be conducted by the individual data source holders according to the specifications given in Section 10.2.2. After the identification of the study population from different data sources, study data from each data source will be extracted. The data extraction will be conducted by the individual data source holders. After data are extracted, the data holders will make data accessible to IQVIA, according to data permits in each respective country. The details of the data permits will be confirmed when the data permits are granted. If the data permits allow, individual level data will be accessed by IQVIA. However, individual level data from some of the data holders (SHI (Germany) and SIDIAP (Spain)) cannot be accessed by IQVIA but will be managed and analysed by the data provider (Team Gesundheit (Germany) and Primary Care Research Institute Jordi Gol (Spain)). All individual level data accessible to IQVIA will not have access to data that allow individuals to be directly identified.

IQVIA will adhere to all local and regional laws on data protection and privacy. IQVIA will also adhere to IQVIA standard operating procedures, and data management for this study will be conducted using standard IQVIA processes. IQVIA will maintain appropriate data storage, including periodic backup of files and archiving procedures and will comply with procedures that include checking electronic files, maintaining security and data confidentiality, following analyses plans, and performing quality checks for all scripts.

The general principles for data management and statistical analyses will be described in detail in the SAP. Therein all data checks to be performed on completeness, plausibility, and consistency of collected data will be described in detail with identification of data discrepancies. IQVIA will perform all data management and statistical analyses using statistical software (SAS version 9.4 or later, or R [version 3.5.0 or later]) or STATA. The data providers conducting the data management and statistical analysis for the study will store the datasets and analytic scripts according to the data provider's procedures. Full audit trail starting from raw data obtained from register holders and ending to statistical tables and graphs in reports will be maintained. Source code of data management and data analyses will be kept for inspection for five years after publication of results. The study may be inspected by AstraZeneca's independent representative(s), scientific committee, or by the competent authorities.

10.7 Data analysis

A full description of the analytical approach will be developed and described in the SAP. Details on data derivations, category definitions, analyses, handling of missing data, and presentation of the study results will be provided in SAP. SAP will be finalised prior to the conduct of the study analyses.

All study results will be presented separately for each country in the study reports, as appropriate when data become available. The final study report will include all descriptive, comparative, exploratory and sensitivity analyses as well as the meta-analysis for all the data sources.

10.7.1 Statistical methods

10.7.1.1 Time-based exposure sets and propensity score matching

Base cohort

The base cohort will be defined using SLE diagnosis within the study period as the inclusion criteria. Anifrolumab exposed patients in the base cohort will consist of individuals who had prior exposure to SLE SOC drugs. Hence, the base cohort will be formed of all patients who have used SLE SOC, some adding-on anifrolumab as incident user, and the others continuing SLE SOC alone.

Time-based exposure sets

Time-based exposure sets will be defined to determine the time-points at which comparability will be established. Time on SLE SOC (i.e., time from the first prescription of SLE SOC for moderate to severe SLE) will be considered as a marker of disease course. For each exposed patient, a time-

based exposure set will be created including all unexposed patients with similar time on SOC as the exposed at the time of anifrolumab initiation. Anifrolumab and SLE SOC prescriptions dates will be used to anchor the exposure sets from the base cohort [88]. The detailed process of time-based exposure set creation is presented in Section 10.1 and in Section 10.2.2.1.

Time-conditional propensity score-based matching

Time-conditional propensity scores will be used to compute, for each patient in each time-based exposure set, the propensity of being exposed to anifrolumab (vs. staying on SLE SOC) as a function of patient characteristics at the exposure risk set date. Variables identified as potential confounders included in Table 6 will be considered for inclusion in the time-conditional propensity score. The steps involved in creation of time-based exposure sets and PS matching are below:

- 1. In the base cohort, each patient is treated as a possible comparator in the beginning until exposure of anifrolumab or censoring due to other reasons.
- 2. The index date for patients in the exposed group is their anifrolumab first exposure date.
- 3. On a timescale of time since start of SLE SOC, for each timepoint where a patient is exposed to anifrolumab, the set of eligible comparators is formed based on time since the start of SLE SOC.
- 4. All patients who are not yet on anifrolumab are eligible for being a comparator. Eligible comparators must have a prescription of SLE SOC within +/- 45 days (wider time intervals may be considered if matches cannot be obtained using this time window) of the respective anifrolumab exposure date, on the time scale of time since start of SOC. The closest SOC prescription date to the anifrolumab exposed patient's index date will be selected as an index date for the matched comparator patient. Patients who are not yet on anifrolumab can therefore be included in several time-based exposure sets.
 - a. For example, if the exposed patient initiates anifrolumab 180 days since start of SLE SOC, eligible comparators with a SOC prescription between 135 days and 225 days since start of SLE SOC will be included in the time-based exposure set.
- 5. For all patients, time-varying PS covariates (for example, SLE severity, SLE activity, comorbidity status, BMI, age etc.) will be updated at each time point corresponding to a time-based exposure set (i.e., at index date).
- 6. The time-conditional propensity score will be fit as a single time-dependent Cox proportional hazards regression or conditional logistic regression model (as appropriate given the data), using all the time-varying and fixed covariates from all the exposure sets.
- 7. Within each time-based exposure set, the model fitted from step 6 will be used to compute time-conditional PS values for the anifrolumab exposed patient and its eligible set of comparators.
- 8. For positivity purposes, within each time-based exposure set, the time-conditional PS value of the exposed patient should be within the range of the time-conditional PS values of the unexposed patients. If this is not the case, the exposure set is eliminated.

- 9. Matching will be done chronologically from SLE SOC start. Up to 3 matches will be selected amongst the SLE SOC comparators within the time-based exposure set based on whose PS scores are the closest to the score of the anifrolumab initiator. Matched comparators will be removed from all subsequent time-based exposure sets.
- 10. The effectiveness of this matching will be assessed. Covariate distributions before and after matching and the associated balance diagnostics will be reported.

Further details regarding the PS computation and matching procedure will be provided in the SAP.

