10.2.1 Study time periods

The study time period for analysis will be based on availability of information from the data sources and on the date of market availability for anifrolumab. The **start of the study period** will be the market launch date of anifrolumab in each country (Table 3); this considers that all data sources included in the study are available for at least 12 months before that date (12 months correspond to the minimum look-back period before index date for confounders and/or risk factors).

The **end of study period**, defined as the last possible day of follow-up when all patients still in the study are censored, will likely differ between countries and will depend on length of data lag in each country at the time when the last data extraction is performed (Table 3). The rationale for this choice is to include all data available from relevant data sources to capture a sufficient number of outcomes and exposures for the primary outcomes at study.

Country	Start of study	Start of	End of	End of	End of study	End of study
	period ^a	enrolment ^b	enrolment for	enrolment	period for SI	period for M
		Date when first	SI outcomes ^c	for M	outcomes ^e	outcomes ^f
		patient can be	Date when last	outcomes ^d	Last possible	Last possible
		enrolled	patient can be	Date of last	day of	day of follow-
			enrolled	patient	follow-up,	up, when all
				enrolled	when all	patients still
					patients still	active are
					included are	censored
					censored	
Denmark	04 May 2022	04 May 2022	30 April 2025	31 May 2028	31 May 2025	31 May 2029
France	19 April 2022	19 April 2022	30 April 2025	31 May 2028	31 May 2025	31 May 2029
Germany	11 March 2022	11 March 2022	30 April 2025	31 May 2028	31 May 2025	31 May 2029
Spain	May 2023 (Tbc)	May 2023 (Tbc)	30 April 2025	31 May 2028	31 May 2025	31 May 2029

Table 3 Relevant dates of the study by country

Abbreviations: SI, serious infection; M, malignancy; Tbc, to be confirmed.

^aAnifrolumab market launch date.

^bStart of enrolment is same for the serious infections and malignancy cohorts.

°For infections the last patient will be included 1 month before the end of study period.

^dFor malignancies the last patient will be included 12 months before the end of study period.

^eCalculated assuming that the final report is due on 30 Nov 2028, assuming a two-year lag time in data availability. Needs to be adapted by country after feasibility study.

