10.2.2 Participants

10.2.2.1 Participants for the main analysis

For data extraction and the creation of study cohorts, a sequential approach will be used as presented in Figure 4 and detailed below. This approach applies to the creation of the cohorts for the main analyses of the primary, secondary, and exploratory objectives.

	Data extraction	
STEP 1	Overall SOURCE population Inclusion criterion: Patients with SLE diagnosis in the study time period	
	Pool of patients exposed and unexposed to anifrolumab from the	overall source population
STEP 2	 STEP 2a: Exposed patients in the SOURCE population Inclusion criteria: First prescription of anifrolumab in the study period (index date) Other inclusion criteria^a 	 STEP 2b: Unexposed patients in the SOURCE population^b Inclusion criteria: Not exposed to anifrolumab Other inclusion criteria are not assessed at this step^b
	Exposed patients in the outcome-specific SOURCE population	
STEP 3	3a. Exposed in the Malignancy 3b. Exposed in the Serious SOURCE population Infection SOURCE population Malignancies' exclusion criteriac Serious infections' exclusion criteriac	ad
	Time-based exposure sets	
	4a. Malignancies' exposure set Patients exposed to anifrolumab (STEP 3a) + Unexposed patients (STEP 2b)	 4b. Serious infections' exposure set Patients exposed to anifrolumab (STEP 3b) + Unexposed patients (STEP 2b)
STEP 4	 Inclusion criteria for unexposed Similar duration of previous exposure to SLE SOC as the anifrolumab patient, at index date No prescription for anifrolumab prior to index date 	 Inclusion criteria for unexposed Similar duration of previous exposure to SLE SOC as the anifrolumab patient, at index date No prescription for anifrolumab prior to index date
	•Other inclusion criteriaª	•Other inclusion criteria ^a
	 Exclusion criteria for unexposed: Malignancies' exclusion criteria^c 	 Exclusion criteria for unexposed: Serious infections' exclusion criteria^d
	STUDY population (for each exposed patient, up to 3 unexposed patient)	nts are selected with the closest PS)
STEP 5	STUDY cohort for Malignancies	STUDY cohort for Serious Infections
	Malignancy cohort = malignancy_exposed + malignancy_unexposed	SI cohort = infection_exposed + infection_unexposed

Figure 4 Overview of the data extraction and definition of the study populations

PS: Propensity-Score; SLE: systemic lupus erythematous; SI: serious infection; SOC: standard of care. ^aOther inclusion criteria:

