- A minimum data availability of 12 months prior to index date.
- Age ≥ 18 years, at index date.
- SLE severity: patients with moderate to severe SLE at index date.
- SLE activity: patients with at least a flare in the 6 months prior to index date.

^bInclusion and exclusion criteria for unexposed patients can only be applied at the creation of the exposure sets (STEP 4) because the time scale will be defined on the SLE duration of the exposed patients. Comparators do not have an index date before the identification of eligible anifrolumab patients.

^cMalignancies' exclusion criteria:

• A diagnosis of any malignancy prior to index date.

^dSerious infections' exclusion criteria

- A diagnosis of any malignancy prior to index date.
- A diagnosis of HIV/AIDS or congenital immunodeficiency prior to index date.
- Organ or bone marrow transplant prior to index date.
- Serious infection in the previous 6 months.

STEP 1 (Data extraction) – Overall source population

Inclusion criteria:

• Patients with SLE diagnosis (10th Revision International classification of diseases [ICD-10] codes M32.X) in the study time period.

STEP 2 – Identification of patients exposed and unexposed to anifrolumab in the overall source population

From the overall source population, exposed patients are selected. All patients not exposed to anifrolumab remain eligible to be comparators. Patients who are later exposed to anifrolumab are eligible to be comparators until then.

Step 2a. Exposed patients in the source population

Inclusion criteria:

- First prescription of anifrolumab in the study period (no anifrolumab prescription prior to index date): date of first anifrolumab prescription will be the **index date**.
- A minimum data availability of 12 months prior to index date.
- Age ≥ 18 years at index date.
- SLE severity (based on the SLE severity algorithm, Section 10.3.3.3): patients with moderate to severe SLE at index date³.
- SLE activity (based on the SLE activity algorithm, Section 10.3.3.3): patients with at least a flare (uncontrolled SLE) in the 6 months prior to index date.

Step 2b. Unexposed patients in the source population

Inclusion and exclusion criteria for unexposed patients can only be applied after identifying eligible exposed patients (at step 4) because unexposed patients do not have an index date before that (the time scale will be defined on the SLE duration of the exposed patients).

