STEP 3 – **Identification of patients exposed to anifrolumab for the outcome-specific source** population

At step 3, the malignancy and serious infection source populations will be created.

Step 3a. Exposed patients in the malignancy source population

Additional exclusion criteria to be applied to the exposed patients:

• A diagnosis of any malignancy prior to index date.

³ According to the SLE severity algorithm, most moderate to severe patients will be those with a previous exposure to SOC indicated for moderate to severe disease. A very small group of patients, defined as having moderate/severe SLE based on the existence of SLE-related comorbidities, will not have a prescription of SOC for moderate/severe SLE.

Step 3b. Exposed patients in the serious infection source population

Additional exclusion criteria to be applied to the exposed patients:

- A diagnosis of any malignancy prior to index date.
- A diagnosis of HIV/AIDS or congenital immunodeficiency prior to index date.
- Organ or bone marrow transplant procedure prior to index date.
- A diagnosis of serious infection in the previous 6 months.

STEP 4 – **Time-based exposure sets**

This step is defined to create the time-based exposure sets, from the outcome-specific source populations. For each patient exposed to anifrolumab (identified in steps 3a and 3b) all unexposed patients from the source population (step 2b) that meet the following criteria will be included as unexposed patients.

Step 4a. Malignancy time-based exposure set

Patients exposed to anifrolumab from the malignancy source population (step 3a) and patients unexposed to anifrolumab (step 2b). Inclusion criteria for patients unexposed to anifrolumab (exposed to SLE SOC):

- At least a prescription of SOC indicated for moderate to severe SLE (Table 14).
- Duration of the previous exposure to SLE SOC similar to the SLE SOC duration of the corresponding exposed patient (+/- 45 days [wider time intervals may be considered if matches cannot be obtained using this time window]), at index date. The **index date** for the patient unexposed to anifrolumab will be the SLE SOC prescription date that will result in length of the SLE SOC treatment closer to SLE SOC treatment of the corresponding exposed patient.
- No prescription for anifrolumab prior to index date.
- A minimum data availability of 12 months prior to index date.
- Age ≥ 18 years at index date.

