- SLE severity (based on the SLE severity algorithm, Section 10.3.3.3): patients with moderate to severe SLE at index date.
- SLE activity (based on the SLE activity algorithm, Section 10.3.3.3): patients with at least a flare (uncontrolled SLE) in the 6 months prior to index date.

Exclusion criteria for patients unexposed to anifrolumab (exposed to SLE SOC):

• A diagnosis of any malignancy prior to index date.

Step 4b. Serious infections' time-based exposure set

Patients exposed to anifrolumab from the serious infection source population (step 3b) and patients unexposed to anifrolumab (step 2b). Inclusion criteria for patients unexposed to anifrolumab (exposed to SLE SOC):

- At least a prescription of SOC indicated for moderate to severe SLE (Table 14).
- Duration of the previous exposure to SLE SOC similar to the SLE SOC duration of the corresponding exposed patient (+/- 45 days, [wider time intervals may be considered if matches cannot be obtained using this time window]), at index date. The **index date** for the patient unexposed to anifrolumab will be the SLE SOC prescription date that will result in length of the SLE SOC treatment closer to SLE SOC treatment of the corresponding exposed patient.
- No prescription for anifrolumab prior to index date.
- A minimum data availability of 12 months prior to index date.
- Age ≥ 18 years at index date.
- SLE severity (based on the SLE severity algorithm, Section 10.3.3.3): patients with moderate to severe SLE at index date.
- SLE activity (based on the SLE activity algorithm, Section 10.3.3.3): patients with at least a flare (uncontrolled SLE) in the 6 months prior to index date.

Exclusion criteria for patients unexposed to anifrolumab (exposed to SLE SOC):

- A diagnosis of any malignancy prior to index date.
- A diagnosis of HIV/AIDS or congenital immunodeficiency prior to index date.
- Organ or bone marrow transplant procedure prior to index date.
- A diagnosis of serious infection in the previous 6 months.

STEP 5 – **Propensity score matching to define the study populations**

From the malignancy and serious infection time-based exposure sets, the respective study cohorts will be created. For each exposed patient, up to three unexposed patients (exposed to SLE SOC) with the closest PS are selected to create the final combinations of exposed-unexposed patients.

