SNDS contains data on the presence and diagnosis date of long-term chronic disease (LTD). LTD is used together with PMSI to identify patients, namely those with SLE. Patients with LTD are eligible for 100% reimbursement of healthcare expenditure. The request for attribution of LTD is made by the general practitioner and it is not mandatory. Thus, it may be missing, for instance, if the medical expenses are already covered by another chronic disease or the treatment is not expensive. Diagnoses are coded using ICD-10.

SNDS also includes demographic data (including age, sex, place of residence, complementary universal health coverage status (as proxy to socio-economic status), date of death), health encounters, dispensations, medical devices, and laboratory tests (without results) [14].

Data from DCIR and PMSI are annually updated and can be linked for each patient. At the time of the feasibility assessment, data were available until the end of 2021.

Study-specific data

In France, market launch for anifrolumab occurred in April 2022 (Table 3). A favourable reimbursement decision has been made by the health assessment authorities in France. Therefore, it is anticipated that anifrolumab will likely be included in the list of high-cost drugs and thus, will be captured in PMSI.

Data on SLE SOC drugs are available, except for voclosporin and mepacrine, which are not marketed in France. Some drugs, such as methotrexate, mycophenolate mofetil, cyclophosphamide, and cyclosporine are available if the oral forms are used. Chloroquine was in

use until the end of September 2022, when the last product was withdrawn from the market. Furthermore, rituximab and immunoglobulin G – administered as IV at the hospital – are available as they are part of the list of high-cost drugs. Only the pen formulation of belimumab, delivered in retail pharmacies, is captured.

Data on overall and specific malignancies are captured through coded diagnoses at the hospital level. This is also true for serious infections in which diagnoses allow for the identification of specific types of serious infections. Data on prescription/administration of IV antimicrobials are available for inpatients if antimicrobials are part of the list of expensive drugs. Dates of diagnoses (inpatients), hospitalisation, discharge and death are available.

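### Cohort entry needs an SLE diagnosis within the study period, not on or before the index date, so patients can be admitted on a post-index code and those coded only before launch dropped

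*Protocol*

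**What the plan says.** The entry rule appears three times in the Protocol. Figure 4 gives it as "Inclusion criterion: Patients with SLE diagnosis in the study time period". Step 1 of section 10.2.2.1 gives it as "Patients with SLE diagnosis (10th Revision International classification of diseases [ICD-10] codes M32.X) in the study time period". The base-cohort text in section 10.7.1.1 reads "The base cohort will be defined using SLE diagnosis within the study period as the inclusion criteria".

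Section 10.2.1 and Table 3 start the study period at anifrolumab launch in each country (2022, or May 2023 to be confirmed for Spain). They end it on 31 May 2025 for serious infections and 31 May 2029 for malignancies.

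Steps 2a, 4a and 4b then set the patient-level criteria. Twelve months of data, age, severity, flare and most exclusions are anchored to the index date; the activity criterion, for example, is "patients with at least a flare (uncontrolled SLE) in the 6 months prior to index date". The SLE diagnosis is not among these anchored criteria. A comparator's index date is itself a treatment date, namely the "SLE SOC prescription date that will result in length of the SLE SOC treatment closer to SLE SOC treatment of the corresponding exposed patient".

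For France, section 10.4.1.2 says that "LTD is used together with PMSI to identify patients, namely those with SLE". LTD is long-term-disease status and PMSI is the hospital discharge file.

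**The concern.** Eligibility should be decided from what is known at the index date. Here the diagnosis criterion is met by a code at any time between launch and the end of follow-up. This has two consequences.

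- A patient diagnosed and coded before launch, with no later code, fails the criterion although the disease is established.
- A patient can meet it only because of something recorded after the index date, when follow-up for serious infection is already running.

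The second is selection on the future. If the qualifying code comes from the admission that is also the outcome, comparators are partly chosen because they had the event. If it comes from a later contact unrelated to the outcome, the patient had to stay alive and under observation until then. Matching on time since first standard-of-care (SOC) prescription and on covariates measured at index addresses neither. The primary hazard ratios of a safety study are at stake, so the rule should not be left to interpretation.

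**Working it through.** No stated figure in the plan depends on this rule, so there is nothing to reproduce. The check sets the passages side by side.

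**1. Does another eligibility criterion supply the missing anchor?** Steps 4a and 4b ask for a SOC prescription, moderate to severe disease at index and a recent flare. Section 10.3.3.3 describes the severity and activity algorithms as built on SLE drugs, SLE-related comorbidities and healthcare use. A flare may be NSAID use or the start of a new SOC drug. Table 14 includes glucocorticoids and methotrexate. The text states no need for an M32 code. Figures 9 and 10 are not reproduced in the text available, so a code requirement inside them cannot be excluded.

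**2. Three hypothetical comparators under the literal wording (dates invented).**

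| Patient | M32 codes | Index date | Literal rule | Rule anchored at index |
|---|---|---|---|---|
| A | 2018 only | 2023 | excluded | eligible |
| B | 2018, then at a 2024 admission | 2023 | admitted through the 2024 code | eligible through the 2018 code |
| C | first code in 2024 | 2023 | admitted | not eligible |

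If the 2024 admission of B or C also carries an infection code, one stay gives both entry and outcome, because section 10.3.2.2 counts an infection diagnosis in any position of a hospital episode. Had B not been admitted in 2024, B would have been treated like A.

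**3. Where is this most direct?** France has 74.56% of the planned sample (Table 13). SLE is found there through LTD status or hospital data, and section 10.4.1.2 says the LTD request is not mandatory and may be missing. For a French patient without LTD, the SLE code has to come from a hospital stay. The documents do not give the share of such patients.

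**4. Which passages conflict with the rule?** Section 10.3.1.2 starts the comparator's SOC episode with a prescription that follows the diagnosis of moderate to severe SLE. Table 6 lists disease duration from diagnosis to study entry, which would be negative for patient C. Section 10.9 explains that comparators are chosen regardless of later anifrolumab initiation so that immortal time is not built in. An entry rule that can be met by a later code does not follow the same principle.

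**5. Illustration, pure assumption.** Let a share s of matched serious-infection comparators qualify only through the outcome admission, with the event at one year. Inputs from section 10.5.2: 39.8 per 1000 person-years, 2 years, 3 × 1,312 = 3,936 comparators.

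- Events = 3,936(1 − s)(1 − exp(−0.0398 × 2)) + 3,936s.
- Person-years = 3,936(1 − s)(1 − exp(−0.0398 × 2))/0.0398 + 3,936s × 1.
- Observed ratio for a true 1.5 = 1.5 × 39.8 / (comparator rate per 1000).

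| s (assumed) | Comparator events | Rate per 1000 | True 1.5 observed as |
|---|---|---|---|
| 0% | 301 | 39.8 | 1.50 |
| 0.5% | 319 | 42.3 | 1.41 |
| 1% | 338 | 44.8 | 1.33 |
| 2% | 374 | 49.9 | 1.20 |
| 5% | 483 | 65.4 | 0.91 |

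The documents give no value for s, and the model leaves out the opposing effect of survival to a later non-outcome code. It shows how sensitive the ratio is to this one route and is not an estimate of the bias.

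**The case against.** The authors evidently meant the diagnosis to come first. Section 10.3.1.2 and Table 6 presume it. Section 10.9 worries about left-censored diagnosis dates, which matters only if historical diagnoses are used. Step 1 is headed as data extraction, and its phrase could mean patients who carry the diagnosis during the period; the pool in Appendix 4.3 was sized on 12-month prevalence. Section 10.3 leaves variable definitions to local protocols and the SAP.

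Much of this stands as evidence of intent, and it weighs against patient C. It does not settle patients A and B, who were diagnosed before launch. None of those passages is an entry criterion. Section 10.6 has the data holders identify the population from section 10.2.2, so the literal text would drive the extraction.

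Three stronger readings are tempting, and the documents do not support them.

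- **That the rule masks a safety signal.** Only the outcome-admission route lowers the hazard ratio. Survival to a later non-outcome code lowers the comparator rate and raises the ratio.
- **That exposed patients receive an SLE code whenever anifrolumab is given.** No passage says so, and section 10.4.1.3 states that German data have no active link between diagnosis and prescribed therapy.
- **That comparators are generally coded only when admitted.** French LTD status, Danish specialty outpatient clinics, German outpatient care and Spanish primary care are all non-admission routes.

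**Conclusion.** The point holds as a fault in a stated eligibility rule. Entry is tied to the study period in three places and to the index date in none. As written, the rule can admit patients on post-index information and drop those coded only before launch, and it disagrees with section 10.3.1.2 and Table 6. The risk is most direct for serious infections in French comparators without a long-term-disease record.

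The documents fix neither the net direction nor the size of any bias. That would need the share of comparators whose only in-period code falls after index, split by whether the code comes from the outcome admission. An open LTD record counted as a diagnosis in the period would shrink the problem. The conclusion rests on the literal text and on the algorithms in Figures 9 and 10 not themselves requiring an SLE code. The rule should be corrected before extraction begins.

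**What to change.** In Step 1, Step 2a, Steps 4a and 4b, and the base-cohort text of section 10.7.1.1, require at least one SLE diagnosis (M32.x, or the source's long-term-disease record) on or before the index date, using all available look-back, for exposed and unexposed patients alike. Align Figure 4. State that no code recorded after the index date may be used for inclusion. This also brings the entry rule into line with section 10.3.1.2 and the disease-duration variable in Table 6.

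The cost is a change of wording and an extraction query that covers diagnoses before launch. Table 26 lists the date of SLE diagnosis as available in all four sources, and Table 7 shows data from 2010 or earlier in each. The change has to precede extraction, because a pre-launch diagnosis that was never extracted cannot be restored at analysis.
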